10 CRITERIA FOR EVALUATION OF STUDY RESULTS

10.1 Criteria for Evaluation of Efficacy

10.1.1 Primary efficacy outcome

The primary efficacy outcome is the percentage of patients who experience one of the following events during the first 28 days:

- All-cause mortality
- Requirement for ICU admission and/or ventilatory support due to COVID-19
- CV complications*:
 - HF or
 - AMI or
 - myocarditis or
 - new sustained or symptomatic arrhythmia or
 - stroke

*see definitions in Appendix 17.8

10.1.2 Secondary efficacy evaluations

The secondary efficacy parameters are listed in section 4.1.4.

To control the family-wise Type I error rate, the Benjamini-Hochberg procedure will be applied.

10.1.3 Other efficacy evaluations

Other efficacy parameters are listed in section 4.1.5

The results of the findings for other endpoints are supportive and not confirmatory on their own. Therefore, the effect of the randomly allocated study treatment on the other efficacy endpoints are reported, in addition to measures of effect sizes, standard errors, confidence intervals, with nominal p values, unadjusted for testing multiplicity.

10.2 Criteria for Evaluation of Safety

The safety parameters of interest are listed in section 4.2.2.

10.3 Description of Patient Groups for Analyses

10.3.1 Intention-to-treat (ITT) Population

The primary analyses will be performed on the ITT population. All patients who were randomized will be included in the ITT analyses.

PROPRIETARY AND CONFIDENTIAL

10.3.2 Per-Protocol Population

The Per-Protocol Set will be a subset of the ITT population who do not present with any major protocol deviations potentially impacting on the primary outcome and who must have a study treatment compliance of > 75%.

11 STATISTICAL METHODS

11.1 Sample Size Estimation

Assuming that 19% of patients qualifying for the study in the placebo group would develop one or more primary outcomes, a treatment effect of lowering the event rate by 50% (i.e., only 9.5% of patients treated with CardiolRx™ would experience a primary outcome event, a two-sided alpha of 0.05 and 80% power, 211 patients per group (422 in total) would be required.

Consideration will be given to adjust the sample size just before the interim analysis, should the observed event rate differ from the assumption above. Consideration will also be given to upgrading the Ordinal Outcome Scale first secondary endpoint to be the primary endpoint should the event rate of the current primary endpoint be significantly lower than the above assumption. This would be carried out in a blinded fashion. If the overall primary event rate is lower than $(19 + 9.5)/2 = 14.25\%$, the sample size will be increased to preserve 80% power to detect a 50% relative reduction with a two-sided alpha of 0.05.

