11.2.1 Primary efficacy analysis

For the primary efficacy analysis, the proportions of patients experiencing at least one primary outcome event as described in section 10.1.1 in the active group will be compared to the proportions of patients experiencing at least one primary event in the placebo group using Fisher's exact test. The proportions will be expressed as percentages. In addition, the 95% confidence interval for the proportion using exact (Clopper-Pearson) estimates will be provided.

A secondary exploratory sensitivity analysis of the primary endpoint will compare time to the occurrence of the first primary event between the two groups using a Cox proportional hazards model. Kaplan-Meier plots for each treatment group will also be generated.

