11.4 Statistical Inference

P-value-based claims about the primary efficacy outcome will be based on $p < 0.05$.

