14.4.2 Changes to protocol and related procedures

Changes to the protocol should only be made in the form of protocol amendments. If substantial changes to the design of the study are made, local IRBs/ERBs should be notified and, if required, approve the change before inclusion of new patients.

The Project Management Team is responsible for the distribution of a protocol amendment to investigators. Investigators are responsible for the distribution of an amendment to all staff involved in the study and to the local IRB/ERB.

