## 6 STATISTICAL METHODS

### 6.1 Sample Size Justification

Assuming that 19% of patients qualifying for the study in the placebo group would develop one or more primary outcomes, a treatment effect of lowering the event rate by 50% (i.e. only 9.5% of patients treated with CardiolRx™ would experience a primary outcome event, a two-sided alpha of 0.05 and 80% power, 211 patients per group (422 in total) would be required.

The protocol contained information to consider an adjustment to the sample size. Due to the early termination of the study no sample size re-estimation will be performed.

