#### 9.1.1 Proportions of Subjects with an Event

All subjects who have met any condition of the composite outcome will be listed.

Due to the early termination of the study no analysis will be performed.

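### The stated 80% power at 211 per group is not the power of the planned Fisher's exact test, which is about 77%

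*Protocol*

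**What the plan says.** Protocol 11.1 starts from a placebo event rate of 19% ("Assuming that 19% of patients qualifying for the study in the placebo group would develop one or more primary outcomes") and a 50% relative reduction, which gives 9.5% on CardiolRx. It then concludes that with "a two-sided alpha of 0.05 and 80% power, 211 patients per group (422 in total) would be required". The synopsis and SAP 6.1 carry the same statement. No test or formula is named in any of the three places.

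The primary analysis is specified in Protocol 11.2.1: the active-group proportion is compared with "the proportions of patients experiencing at least one primary event in the placebo group using Fisher's exact test". The synopsis names the same test. Protocol 11.4 sets the threshold: "P-value-based claims about the primary efficacy outcome will be based on" p < 0.05.

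Protocol 11.1 also has a blinded re-estimation rule. If the pooled event rate is below 14.25%, "the sample size will be increased to preserve 80% power to detect a 50% relative reduction with a two-sided alpha of 0.05". Again no test is named.

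The SAP was written after early termination. On re-estimation it says "Due to the early termination of the study no sample size re-estimation will be performed" (6.1), and on the primary endpoint "Due to the early termination of the study no analysis will be performed" (9.1.1).

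**The concern.** A reader who sees one primary test in the protocol will take the stated 80% as the power of that test. Fisher's exact test is conservative with binary data at these sample sizes. A sample size solved with an ordinary normal-approximation formula will therefore usually fall short of its nominal power once Fisher's test is applied. If so, the design carries a larger type II risk than it declares. The re-estimation rule would carry the same shortfall forward if it used the same formula.

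**Working it through.** **Inputs.** Placebo rate p1 = 0.19, active rate p2 = 0.095, two-sided alpha 0.05, power 80% and 211 per group are from Protocol 11.1. Allocation is 1:1 (Protocol 6.1). The test is Fisher's exact (11.2.1) at p < 0.05 (11.4). All randomized patients are analysed (10.3.1), and no dropout allowance is stated, so every outcome is taken as observed.

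**Step 1: reproduce 211.** The pooled-variance normal approximation without continuity correction is

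n = [z(0.975)·√(2·p̄(1−p̄)) + z(0.80)·√(p1(1−p1) + p2(1−p2))]² / (p1−p2)²

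with p̄ = (0.19 + 0.095)/2 = 0.1425.

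- First term: 1.960 × √(2 × 0.1425 × 0.8575) = 1.960 × 0.4944 = 0.9689
- Second term: 0.8416 × √(0.1539 + 0.0860) = 0.8416 × 0.4898 = 0.4122
- n = (1.3811)² / 0.095² = 1.9075 / 0.009025 = 211.4

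The same approximation gives 79.9% power at 211. Other common formulas do not give 211: unpooled variance 209, arcsine 207, continuity-corrected 232. So 211 is consistent with an uncorrected chi-square calculation. That is an inference, since the documents do not state the formula.

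**Step 2: power of the planned test at 211 per group.** Exact power is the sum, over all pairs (x, y) with two-sided Fisher p < 0.05, of Bin(x; 211, 0.19) × Bin(y; 211, 0.095).

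| Test at 211 per group | Exact power |
|---|---|
| Uncorrected chi-square | 80.6% |
| Continuity-corrected chi-square | 76.6% |
| **Fisher's exact, two-sided** | **76.8%** |

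The two usual ways of forming a two-sided Fisher p-value (summing tables no more likely than the one observed, or doubling the smaller tail) give the same 76.8%. The shortfall is 80 − 76.8 = 3.2 points, and the type II risk is 100 − 76.8 = 23.2%. The loss comes from conservatism: with a common event rate of 14.25% in both groups, the true type I error of Fisher's test at this size is about 3.7%, not 5%.

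**Step 3: sample size for 80% with Fisher's test.** Exact power rises unevenly with n:

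| n per group | 211 | 220 | 226 | 227 | 228 | 229 | 230 |
|---|---|---|---|---|---|---|---|
| Power | 76.8% | 78.7% | 79.8% | 80.0% | 79.9% | 80.1% | 80.3% |

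It first touches 80% at 227, dips at 228, and stays above 80% from 229 up to 239, the largest size checked. At 229 per group the total is 458, which is 458 − 422 = 36 more than planned.

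**Step 4: scale.** Keep 211 per group and a 50% reduction, and vary the placebo rate:

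| Placebo rate | 18% | 19% | 20% | 20.5% |
|---|---|---|---|---|
| Fisher power | 74.0% | 76.8% | 79.4% | 80.7% |

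**Step 5: the re-estimation rule.** Assume the rule used the formula in Step 1 with a 50% reduction, so that p1 = (4/3) × the pooled rate.

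| Pooled rate | p1 vs p2 | n per group | Fisher power |
|---|---|---|---|
| 12% | 16% vs 8% | 258 | 76.9% |
| 10% | 13.3% vs 6.7% | 317 | 76.9% |
| 7.5% | 10% vs 5% | 435 | 77.1% |

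On that assumption the rule would hold power near 77%, not 80%.

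**The case against.** The calculation itself is hard to dispute. The case against acting on it has five parts.

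- **211 is not a miscalculation.** It is right for an uncorrected two-proportion test, and 11.1 never says the 80% belongs to Fisher's test. This stands as a description: the defect is a mismatch between the planning formula and the named analysis. It does not rescue the 80%, because no other primary test is planned.
- **Nothing now depends on it.** The SAP drops the primary test, the interim analysis and the re-estimation, so no primary p-value will be produced and 422 is no longer a target. This stands and limits the weight of the point. SAP 6.1 nonetheless repeats the 80% statement while marking the re-estimation beside it as dropped.
- **76.8% assumes complete outcomes.** Protocol 11.6 plans multiple imputation with Rubin's rule for missing primary outcomes, so with missing data the planned p-value would not be a plain Fisher p. That is true, and the condition should be stated. The protocol's own figure rests on the same basis, and missing outcomes would not be expected to close the gap: with only 200 per group observed, Fisher's power is 74.1%.
- **The gap is small.** It is about the effect of a one-point error in a 19% assumption for which 11.1 gives no source. This too stands. But a placebo rate is uncertain by nature, whereas the power of a named test at stated rates can simply be computed.
- **A design restated at 77% has no 80% to preserve.** The re-estimation wording would sit awkwardly beside the corrected figure, with a step in required size at a pooled rate of 14.25%. This is fair as a drafting point. It is met by wording the 80% in that rule as a target under Fisher's test.

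**Conclusion.** The concern holds. At 211 per group, 19% vs 9.5% and two-sided alpha 0.05, the planned Fisher's exact test has 76.8% power, not 80%. The risk of missing the assumed effect is about 23%, not 20%, and about 229 per group would be needed for 80%. These figures use only the protocol's own inputs and assume outcomes observed in all 422 patients. The origin of 211 in an uncorrected chi-square formula is inferred. The shortfall is modest and affects no reported result. What is wrong is a design figure that the protocol states and the SAP still repeats.

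**What to change.** - **Synopsis, Protocol 11.1 and SAP 6.1:** restate the power as about 77% for Fisher's exact test with 211 per group, at 19% vs 9.5% and two-sided alpha 0.05, with outcomes observed in all patients. In the SAP, attribute the test to the protocol, since the SAP no longer runs it.
- **Synopsis and Protocol 11.1:** add that any sample size re-estimation aimed at 80% power must be computed for Fisher's exact test.

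The cost is wording only. The protocol text would change through an amendment, as 14.4.2 requires ("Changes to the protocol should only be made in the form of protocol amendments"). The primary test, the sample size and the planned outputs stay as they are. The one drawback is a slightly less favourable stated power.

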11.2 Efficacy Analyses

Descriptive statistics will be used to compare baseline characteristics between the two groups. Continuous variables will be expressed as mean \pm SD, categorical variables will be expressed in counts with percentages.

11.2.1 Primary efficacy analysis

For the primary efficacy analysis, the proportions of patients experiencing at least one primary outcome event as described in section 10.1.1 in the active group will be compared to the proportions of patients experiencing at least one primary event in the placebo group using Fisher's exact test. The proportions will be expressed as percentages. In addition, the 95% confidence interval for the proportion using exact (Clopper-Pearson) estimates will be provided.

A secondary exploratory sensitivity analysis of the primary endpoint will compare time to the occurrence of the first primary event between the two groups using a Cox proportional hazards model. Kaplan-Meier plots for each treatment group will also be generated.

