As the severity of the illness increases, complications become more frequent. Patients in ICU may develop severe hypoxemia not readily controlled even with the help of a respirator. In some, this may reflect the development of acute respiratory distress syndrome (ARDS) which may be fatal (Driggin et al. 2020). It has also been noted that patients with COVID-19 who become increasingly ill, are more likely to develop pulmonary embolism (P. P. Liu et al. 2020); a recent study has reported that the incidence of pulmonary embolism in patients with COVID-19 and admitted to the ICU is twice that of ICU-admitted patients without COVID-19 a year earlier (Poissy et al. 2020). In general, there is a hyper-thrombotic state and in some patients, frank disseminated intravascular coagulation (DIC) develops (P. P. Liu et al. 2020; Griffin et al. 2020). A more recent publication in the New England Journal of Medicine described distinctive pulmonary vascular features, consisting of endothelial injury associated with intracellular virus and disrupted cell membranes (Ackermann et al. 2020). These features in the pulmonary vasculature were associated with widespread thrombosis, which was much more common than that observed in patients with influenza. Each of these complications significantly increases the mortality risk for patients with COVID-19.

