9 CONDUCT OF THE STUDY

9.1 Scheduling of Study Procedures

Patients hospitalized for COVID-19 with a prior history of CVD or at least one risk factor for CVD will be screened.

Day 0-1 -- Baseline assessments and Randomization and start of study medication

The following evaluations will be performed a baseline:

- Written informed consent
- Clinical assessment
- Demographics
- Medical History/Current conditions, including prior CV events and interventions
- Concurrent medication and CV medication history for the previous 24 weeks
- C-SSRS
- Vital signs, including heart rate (HR), blood pressure, height and weight
- Chest X-ray
- 12-lead ECG, including QTc interval assessment
- LVEF by echocardiography
- Assessment of Ordinal Outcome Scale
- Local laboratory assessments, including CBC, AST/ALT, alkaline phosphatase, bilirubin, creatinine/eGFR, INR, serum pregnancy test (in women with child-bearing potential only), glucose, total cholesterol, lymphocyte count and LDH
- Retention of frozen samples for hs-troponin, NT-proBNP, D-dimer, hs-CRP, ferritin, TNF-alpha, IL-1 beta, IL-6, IL-10 and additional parameters of interest
- Retention of frozen samples for CBD levels

Randomization and start of study medication (2.5 mg/kg b.i.d.) in the evening of Day 1 after all baseline assessments have been completed and all eligibility criteria are met. Randomization must be no later than 96 hours after hospital admission. Patients awaiting planned admission to hospital in an emergency room for less than 96 hours can be screened and enrolled into the trial.

Day 3

- Vital signs, including HR and blood pressure
- 12-lead ECG, including QTc interval assessment 5 hours post morning dose (time window 3.5 – 6 hours)
- Assessment of Ordinal Outcome Scale
- AE and SAE recording
- Recording of changes in concomitant medications
- Study drug dose increase to 5.0 mg/kg b.i.d., if previous dose is well-tolerated
- Study drug accountability
- Retention of frozen samples for hs-troponin, NT-proBNP, D-dimer, hs-CRP, ferritin, TNF-alpha, IL-1 beta, IL-6, IL-10 and additional parameters of interest

- Retention of frozen samples for CBD levels

Day 5

- Vital signs, including HR and blood pressure
- 12-lead ECG, including QTc interval assessment 5 hours post morning dose (time window 3.5 – 6 hours)
- Assessment of Ordinal Outcome Scale
- AE and SAE recording
- Recording of changes in concomitant medications

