11.2.2 Secondary Efficacy Analyses

The first secondary efficacy analysis will be analyzed using the F-S test (Finkelstein and Schoenfeld 1999). This method compares each subject to every other subject in a pairwise manner following the ranking of the first secondary endpoint (Ordinal Outcome Scale):

- 1) not hospitalized and no limitations of activities;
- 2) not hospitalized, with limitation of activities, home oxygen requirement, or both;
- 3) hospitalized, not requiring supplemental oxygen and no longer requiring ongoing medical care
- 4) hospitalized, not requiring supplemental oxygen but requiring ongoing medical care
- 5) hospitalized, requiring any supplemental oxygen;
- 6) hospitalized, requiring noninvasive ventilation or use of high-flow oxygen devices;
- 7) hospitalized, receiving invasive mechanical ventilation or extracorporeal membrane oxygenation (ECMO);
- 8) MI or stroke diagnosed since randomization
- 9) Death

The F-S test is based on the sum of 'scores' of subjects in the CardiolRx™ group. Where the score is 1, -1 or 0 according to whether the subject is the winner, the loser or tied, respectively, according to the hierarchy above.

In addition, the CardiolRx™ to placebo Win ratio (WR) will be calculated, as described by Pocock.(Pocock et al. 2012) For this statistic, every subject in the CardiolRx™ group is compared to every subject in the placebo group in a pairwise manner following the ranking of the first secondary efficacy endpoint. The WR is the number of pairs with CardiolRx™ subject 'wins' divided by the number of pairs with placebo subject 'wins'. The associated 95% CI will be based on the F-S test statistic to ensure consistency between the CI and the F-S test. A 95%CI for the WR entirely above 1 indicates a better outcome in the CardiolRx™ group.

Changes in hs-troponin and TNF-alpha from baseline to peak elevation during the 28-day treatment period between the two treatment groups will be analyzed using an ANCOVA with the baseline value as covariate.

Treatment effect estimates and 95% confidence intervals will be determined.

To control the family-wise Type I error rate, the Benjamini-Hochberg procedure will be applied to all secondary efficacy analyses.

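### The protocol's primary and first secondary comparisons leave out the baseline Ordinal Outcome Scale score; stratifying by it would cost almost nothing and could add power, mainly for the ordinal endpoint

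*Protocol*

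**What the plan says.** **Primary (Protocol 11.2.1).** The plan is that "the proportions of patients experiencing at least one primary outcome event as described in section 10.1.1 in the active group will be compared" with the placebo proportion by Fisher's exact test. No covariate or stratum is named, and none is named for the Cox sensitivity analysis.

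**First secondary (Protocol 11.2.2).** Of the F-S test the protocol says: "This method compares each subject to every other subject in a pairwise manner following the ranking of the first secondary endpoint". The win ratio likewise uses every active-placebo pair. In the same section, hs-troponin and TNF-alpha are adjusted for their own baseline by ANCOVA.

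**Baseline score.** The Day 0-1 list in Protocol 9.1 includes "Assessment of Ordinal Outcome Scale", and 9.2.8 and the schedule in 17.2.1 agree. Randomization (6.4) is stratified by center only.

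**Prognosis.** The nearest statement is in Protocol 3.3: "As the severity of the illness increases, complications become more frequent". No figure links the baseline score to the composite or to the later score.

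**Sample size (Protocol 11.1).** "Assuming that 19% of patients qualifying for the study in the placebo group would develop one or more primary outcomes", and that "only 9.5% of patients treated with CardiolRx™ would experience a primary outcome event", with "a two-sided alpha of 0.05 and 80% power", the protocol concludes that "211 patients per group (422 in total) would be required". The same section names the ordinal endpoint as a possible replacement primary if events are too few.

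**SAP.** Sections 6.2 and 6.4 confine testing to the markers because the study stopped early. Section 9.1.1 only lists primary events, and 9.2 drops the win ratio.

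**The concern.** Eligible patients may enter on no oxygen, on oxygen, or on high-flow or non-invasive support; only invasive ventilation, current or imminent, is excluded. If entry level is related to outcome, a pair made up of a patient admitted on high-flow oxygen and one admitted on room air differs partly because of where each started. An all-pairs comparison counts that difference as noise. The ordinal endpoint is analysed without its own baseline value, while the two markers in the same section are adjusted for theirs, and no reason is given for the difference.

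Severity is not a randomization factor, so chance imbalance in it stays uncorrected. Power is at stake for both comparisons. It matters more for the ordinal endpoint, where the later score may depend closely on the starting score and which might have become primary.

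**Working it through.** **1. Inputs.** From Protocol 11.1: 19% versus 9.5%, two-sided alpha 0.05, 80% power, 211 per group. Not in the documents, so assumed: the mix of baseline levels, the odds ratio (OR) per level, the placebo distribution of the ordinal score at Day 28, and the treatment effect on that score.

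**2. The stated sample size.** Pooled normal approximation, no continuity correction, mean rate (0.19 + 0.095)/2 = 0.1425:

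n = [1.960 √(2 × 0.1425 × 0.8575) + 0.842 √(0.19 × 0.81 + 0.095 × 0.905)]² / 0.095²
= [0.969 + 0.412]² / 0.009025 ≈ 211.4

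Rounded up this is 212; the stated 211 is in line with it, and power at 211 is 79.9%. The figure therefore corresponds to an unadjusted, uncorrected test.

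**3. The test actually planned.** Exact enumeration for Fisher's test at 211 per group gives 76.8% power, with a true type I error of 3.7% at a common rate of 14.25%. At 230 per group its power is 80.3%.

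**4. Primary endpoint, stratified.** Simulation with 211 per arm, 6000 runs and three baseline levels in mixes of 25/60/15, 40/50/10 and 10/80/10%. Log-odds of an event are linear in level, and overall rates are held at 19% and 9.5%. For example, with the first mix and OR 3, placebo risks are 7.1, 18.6 and 40.6%. The CMH statistic is [Σ(aₛ − Eₛ)]² / ΣVₛ over levels s, where aₛ is the number of active-arm events and Eₛ and Vₛ are its hypergeometric mean and variance, without continuity correction. Power (%), range over the three mixes:

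| OR per level | Fisher | Unadjusted chi-square | CMH by level | CMH minus chi-square |
|---|---|---|---|---|
| 1 | 76.9-78.0 | 80.9-81.4 | 80.6-81.3 | -0.3 to -0.1 |
| 2 | 76.2-77.3 | 79.9-81.0 | 80.6-81.6 | 0.4-0.8 |
| 3 | 76.7-77.1 | 80.5-80.7 | 81.8-83.0 | 1.3-2.4 |
| 5 | 76.4-77.6 | 80.2-81.2 | 82.8-85.8 | 2.6-4.6 |
| 8 | 76.1-77.9 | 79.7-81.6 | 85.7-88.0 | 4.1-7.8 |

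The last column is the effect of the baseline score. The step from Fisher to chi-square, 3.4 to 4.1 points in every scenario, has nothing to do with severity. With no treatment effect, the CMH test rejected in 5.2-5.4% of runs and Fisher's in 3.8%; the simulation standard error there is about 0.3 points.

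**5. Ordinal endpoint, stratified.** Simulation with 211 per arm and 5000 runs, scoring the scale once at Day 28. Assumed placebo distribution over levels 1 to 9: 45/28/2/3/6/3/3/2/8%. The Wilcoxon test stands in for F-S on a single ordinal score, and the van Elteren test is its stratified form. Assumed treatment ORs are 1.65 and 1.8, with the first two mixes. Power (%), unstratified → stratified:

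| OR per level | 25/60/15, OR 1.65 | 25/60/15, OR 1.8 | 40/50/10, OR 1.65 | 40/50/10, OR 1.8 |
|---|---|---|---|---|
| 1 | 77.0 → 77.0 | 88.9 → 88.9 | 77.9 → 77.9 | 88.0 → 87.7 |
| 2 | 75.5 → 77.2 | 86.5 → 88.2 | 74.0 → 76.6 | 86.1 → 87.9 |
| 3 | 70.9 → 77.4 | 83.6 → 88.3 | 70.0 → 75.8 | 82.7 → 86.9 |
| 5 | 63.9 → 73.8 | 75.2 → 85.7 | 62.2 → 74.8 | 75.3 → 86.1 |

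The gains are about 2 points at OR 2, 4-7 at OR 3 and 10-13 at OR 5. A second simulation (3000 runs, treatment log-odds 0.5) is used only for the upper end. At 1.8 log-odds per level, an OR of about 6, power rose from 54% to 68%, a gain of 14 points.

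**6. Chance imbalance.** If 15% enter at level 6 (assumed), the standard error of the between-arm difference is √(2 × 0.15 × 0.85/211) = 3.5 points. An imbalance of 5 points or more then has a probability of about 15% (z = 1.44, two-sided).

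**The case against.** **The tests are not being run.** This is correct. The SAP withdraws both, so a reader who infers that the analysis now planned loses power would be wrong.

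**Prognostic value is not documented.** This also stands. The sentence in Protocol 3.3 leads into complications of ICU patients, not the entry score of non-critical ones, and eligibility narrows that score to about levels 3-6. A reader might take it as established that the score predicts outcome; the documents support only an expectation.

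**The endpoint definition may work against a gradient.** Appendix 17.8.1 counts a new or recurrent need for oxygen or CPAP. A level 4 patient can have an event by starting cannula oxygen with saturation below 94%, whereas a level 5 patient is already on oxygen. That could flatten or partly reverse the relation assumed above for the primary. It weakens the high-OR rows, but stratification needs no assumed direction, and with no relation at all (the OR 1 row) nothing material is lost.

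**Unadjusted tests are valid.** They are: type I error is controlled, and chance imbalance is not bias. The point is efficiency, not error. That does not remove the case for using a value already collected, least of all for the ordinal endpoint.

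**The primary gain is mostly about Fisher's test.** At moderate prognostic strength this is so, as step 4 shows. The whole gap between 77% and 82-83% cannot be put down to the missing baseline score.

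**Conclusion.** The point holds for the protocol as designed. Neither comparison uses a baseline score scheduled for every patient.

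- **Primary:** Fisher's test has 76.8% power against the stated 80%. Stratified CMH has about 81-83% at OR 1-3 per level and about 83-86% at OR 5. At OR 1-3 the adjustment itself supplies only about 0-2.4 points.
- **Ordinal endpoint:** the stronger case, with about 2 points at OR 2, 4-7 at about 3 and 10-14 at 5-6.
- **Uninformative score:** essentially no loss for either endpoint.

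The rates, alpha and sample size are the protocol's. The level mix, OR per level, Day 28 distribution and ordinal treatment effect are assumptions, and missing outcomes were not modelled.

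A reader might extend the argument to the marker ANCOVA in SAP 9.2, the only testing that remains. The documents do not support that as a needed change: those models already adjust for the marker's own baseline, and no gain from adding clinical severity has been shown.

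**What to change.** In the protocol, and in any restart or successor trial:

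- **11.2.1:** test the primary endpoint by CMH, without continuity correction, stratified by baseline ordinal level (4 or lower, 5, 6). Report the Mantel-Haenszel risk difference with a 95% CI. Keep Fisher's test as a sensitivity analysis.
- **11.2.2:** stratify the F-S test and win ratio by the same levels, state the stratum weights, and base the confidence interval on the stratified statistic.
- **Both:** fix in advance, before unblinding, the rule for merging a sparse level with its neighbour and for placing a patient whose baseline score is missing.

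The SAP needs no change on this account. Baseline level in the marker ANCOVA should be left out or labelled optional.

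The cost is wording only, since the score is already scheduled at Day 0-1. The one practical drawback is a possible merger of sparse levels.
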